6.4.4.4 Secondary analyses of neutralization magnitude-breadth curves

Superiority comparisons of vaccine regimens

Simultaneous 95% CIs about the mean-differences in AUC-MBs for each vaccine regimen versus pooled placebo will be reported. These CIs are computed as the estimated mean-difference plus or minus $t_{N-2,025}$ multiplied by the square-root of $S_2 (1/n_1 + 1/n_2)$, where $t_{N-2,025}$ is the 97.5th percentile of a t-distribution with $N - 2$ degrees of freedom, where N is the total number of vaccine recipients evaluated (summing over the two vaccine regimens). In addition, S_2 is an estimate of the common sample variance of the AUC-MB, whereas n_1 and n_2 are the sample sizes of evaluable participants for vaccine regimens 1 and 2 being compared. If the 95% CI comparing the two vaccine arms excludes zero then the two vaccine arms have a significant difference bounding the false positive rate at 5%. Nominal (unadjusted) 95% CIs comparing the vaccine arms will also be reported.

Omnibus comparison of magnitude-breadth distributions

The analyses of magnitude-breadth described above are based on the endpoint area-under-the-curve, which is interpreted as the average \log_{10} IC50 to the set of isolates in the test panel. Use of this endpoint is maximally statistically powerful if 1 vaccine arm has greater magnitude and breadth than the comparator vaccine arm, but may miss an effect wherein 1 vaccine arm has greater magnitude and the comparator vaccine arm has greater breadth. Therefore, a secondary analysis may compare the distribution of magnitude-breadth curves among vaccine arms using the test statistic $\max|B_d^G|$ from Huang, et al (62) (see page 85), which is designed to detect general differences in magnitude-breadth curve distributions.

Selecting the best vaccine regimen

The best vaccine regimen will be deemed as that with the greatest value of the $\max|B_d^G|$ test statistic comparing its distribution of magnitude-breadth curves versus the pooled placebo group.

Superiority comparisons of vaccine regimens

Similarly, the $\max|B_d^G|$ test statistic will be used to compare the distribution of magnitude-breadth curves between the two vaccine regimens. Nominal (unadjusted) 95% CIs comparing the two vaccine arms will also be reported.

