3.2 Secondary Objectives and Endpoints

Secondary objective 1:

- To evaluate the serum IgG binding antibody responses to Env proteins elicited by each vaccination regimen

Secondary endpoint 1:

- Magnitude and breadth of serum HIV-1 Env-specific IgG responses assessed by Binding Antibody Multiplex Assay two weeks after the last vaccination

Secondary objective 2:

- To evaluate the serum neutralizing antibody responses elicited by each vaccination regimen in Part B

Secondary endpoint 2:

- Serum neutralizing antibody responses against Tier 1A, Tier 1B, and selected Tier 2 viruses, assessed by TZM-bl assay, two weeks after the last vaccination in Part B

Secondary objective 3:

- To evaluate each vaccination regimen with specific antibody assays to measure correlates of risk identified in the RV144 trial

Secondary endpoint 3:

- Breadth of gp70-V1V2 IgG and gp120 IgA, assessed by Binding Antibody Multiplex Assay, and ADCC activities against HIV-1 subtypes A, B, C and A/E two weeks after the last vaccination in Part B

Secondary objective 4:

- To evaluate HIV-specific T-cell responses elicited by each vaccination regimen

Secondary endpoint 4:

- Frequency, magnitudes and quality of HIV-1 specific CD4+ and CD8+ T-cell responses as measured by ICS two weeks after the last vaccination

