10 IMMUNOGENICITY TABLES AND FIGURES, BY ASSAY

10.1 Binding Antibody Multiplex Assay (BAMA)

Serum HIV-1-specific IgA and IgG antibody binding responses will be measured at a 1:10 dilution for IgA and 1:50 dilution for IgG, respectively, against various antigens on a Bio-Plex instrument (Bio-Rad) using a standardized custom HIV-1 Luminex assay (Tomaras and Yates et al., J Virology 2008). The readout is background-subtracted mean fluorescence intensity (MFI), where background refers to a plate-specific background measure. Net MFI is MFI minus Blank, where 'Blank' refers to a sample-specific background measure.

BAMA testing will be performed on all participant serum samples collected from Part A, study Group 1 at visits 2 (Month 0) and 5 (Month 2.5, 2 weeks post the 2nd vaccination) and from Part B: study Groups 2 and 3 at visits 12 (Month 0) and 22 (Month 8.5, 2 weeks post the 5th last vaccination). Specimens from other timepoints as well as other HIV antigens and antibody isotypes may be assayed based on the results of the initial assay. If sufficient immunogenicity is observed for the primary analysis antigens, additional assays will be performed using the exploratory antigens.

The following table lists the antigens for the primary analysis.

Panel	Antigen	Clade	Isolate
Vaccine Recombinant Protein	gp120	A	IgG/IgA
	gp120	B	IgG/IgA
	gp120	C	IgG/IgA
	gp120	AE	IgG/IgA
gp120 Breadth Panel	51802_D11gp120.avi/293F	A1	IgG
	BORI_D11gp120.avi/293F	B	IgG
	TT31P.2792_D11gp120.avi/293F	B	IgG
	B.6249_D11gp120/293F	B	IgG
	A244_D11gp120_avi	CRF01-AE	IgG
	254088_D11gp120.avi/293F	CRF01-AE	IgG
	CNE20_D11gp120.avi/293F	CRF07-BC	IgG
	BJOX002_D11gp120.avi/293F	CRF07-BC	IgG
gp70 V1V2 Breadth Panel	gp70-191084_B7_V1V2	A	IgG
	gp70_B.CaseA_V1_V2	B	IgG
	gp70-RHPA4259.7V1V2	B	IgG
	gp70-62357.14_V1V2	B	IgG
	gp70-700010058_V1V2	B	IgG
	gp70-TT31P.2F10.2792_V1V2	B	IgG
	gp70-BF1266_431a_V1V2	C	IgG
	gp70-7060101641_V1V2	C	IgG
	gp70-96ZM61.01_V1V2	C	IgG
	gp70-0014282.42_V1V2	C	IgG
	gp70-CAP210.2.00.E_8_V1V2	C	IgG

	gp70-TV.21 V1V2	C	IgG
	gp70-Ce1086 B2 V1V2	C	IgG
	gp70-CM244.ec1 V1V2	CRF01 AE	IgG
	gp70-C2101.c01 V1V2	CRF01 AE	IgG
	gp70-BJOX002000.03.2 V1V2	CRF07-BC	IgG
Consensus gp140/gp120	Con S gp140 CFI	M	IgG/IgA
	Con 6 gp120/B	M	IgG/IgA
	1086_DCgp120.avi/293F	C	IgG/IgA
	gp41		IgG/IgA
	P24	B	IgG/IgA
	A1.con.env03 140 CF	A	IgG/IgA
	00MSA 4076 gp140	A	IgG/IgA

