The following table lists the antigens for exploratory analysis if sufficient immunogenicity responses are observed (for Part B only).

Panel	Antigen	Clade	Isolate
Extended Clade C gp120 Panel	1394C9_G1.D11gp120.avi	C	IgG
	1428_D11gp120.avi/293F	C	IgG
	1641A7_D11gp120.avi/293F	C	IgG
	CAP210_D11gp120.avi/293F	C	IgG
	CAP45_D11gp120.avi/293F	C	IgG
	Ce0042_D11gp120.avi/293F	C	IgG
	CH505TF_D7gp120.avi/293F	C	IgG
	Du156_D11gp120.avi/293F	C	IgG
	96XM651.D11gp120.avi	C	IgG
	TV1c8_D11gp120.avi/293F	C	IgG
Extended Clade C V1V2 Panel	gp70-CAP45.2.00.G3 V1V2	C	IgG
	gp70-1294C9G1_V1V2	C	IgG
	gp70-1012.11.TC21.3257 V1V2	C	IgG
	gp70-1051.12.C22 V1V2	C	IgG
	gp70-Ce1176 V1V2	C	IgG
	gp70-Ce704010042_2ES V1V2	C	IgG
	gp70-ConcC V1V2	C	IgG
	gp70-DU156.12.V1V2	C	IgG

Several criteria are used to determine if data from an assay are acceptable and can be statistically analyzed. The blood draw date must be within the allowable visit window as determined by the protocol. Second, if the blank bead negative control exceeds 5,000 MFI, the sample will be repeated. If the repeat value exceeds 5,000 MFI, the sample will be excluded from analysis due to high background.

Samples from post-enrollment visits are declared to have a positive response if they meet three conditions:

1. The net MFI values \geq antigen-specific cutoff (based on the 95th percentile of the baseline net MFI values that are greater than/equal to 100 but less than 6,500). If the cutoff is greater than 5,000 net MFI, then the antigen will be excluded from analysis.
2. The net MFI values are greater than 3 times the baseline net MFI values.
3. The MFI values are greater than 3 times the baseline MFI values.

For each of gp120 breadth panel and gp70 V1V2 breadth panel, magnitude-breadth (MB) and AUC-MB will be calculated for each participant by isotype and post-vaccination timepoint.

Contingent upon these results, samples may be titrated to calculate antibody titers (EC50/AUC), in which case geometric mean titers will be compared.

The treatment arm of receiving 2 protein/GLA-SE vaccines is labelled as T1, the treatment arm of receiving 3 DNA prime vaccinations and 2 DNA+Protein/GLA-SE boost vaccinations in Group 2 is labelled as T2, and the treatment arm of receiving 5 DNA+Protein/GLA-SE vaccinations in Group 3 is labelled as T3. The placebo arm in Part A is labelled as P_A. The placebos in Groups 2 and 3 in Part B are pooled and the treatment arm is labelled as P.

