The binding antibody response rates will be compared between treatment arms within each timepoint using Barnard exact test. The response magnitudes, AUC-MB will be compared between treatment arms within each timepoint using Wilcoxon rank sum test. The comparisons of response rates between timepoints within each of treatment arms will be performed using McNemar's test if binding antibody responses will be measured at multiple timepoints.

Similarly, the comparisons of binding antibody response magnitudes, AUC-MB between timepoints within each of treatment arms will be compared using Wilcoxon signed rank test.

If antibody titers (EC50/AUC) data are available, two sample t-test will be used to compare log-titers (EC50/AUC) between two treatment arms within each timepoint and paired t-test will be used to compare log-titers between timepoints within each of treatment arms.

The following tables and figures are generated separately for Part A and Part B unless are specified otherwise.

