10.1.1 List of Tables

- The binding antibody positive response rates by isotype, antigen, visit and treatment arm
- Summary statistics for magnitudes among the positive responders by isotype, antigen, visit and treatment arm
- Summary statistics for AUC-MB by isotype, breadth panel, visit, and treatment arm
- The comparisons of response rates between T2 and T3 by isotype, antigen, and visit
- The comparisons of response magnitudes between T2 and T3 by isotype, antigen, and visit
- Lists of the positive responders and the magnitudes for those participants
- The comparisons of AUC-MB between T2 and T3 by isotype, breadth panel, and visit
- Geometric mean and 95% CI of titers (EC50/AUC) by isotype, antigen, visit, and treatment arm. 95% CI will be calculated based on a normal approximation for log-transformed titers.
- The comparisons of titers (EC50/AUC) between T2 and T3 by isotype, antigen and visit.
- The comparisons of AUC-MB of titers (EC50/AUC) between T2 and T3 by isotype, breadth panel, and visit

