A response is considered positive if the neutralization titer is above a pre-specified cutoff. Magnitude of response will be measured by the natural log of the ID50 and ID80 titer. An aggregate measure of response will be calculated as the area-under-the-magnitude-breadth curve (AUC-MB), which is equivalent to the mean log titer across all viruses in tier 1B and tier 2. If a titer is left censored, half the left censor limit will be used as the titer value.

Neutralization titers will be measured on the primary immunogenicity samples at visit 22 (at week 34, 2 weeks post the 5th vaccination) from all 48 Part B participants. Specimens from other time points may also be analyzed at the discretion of the HVTN Laboratory Program, which may be contingent on the results of the primary immunogenicity time point. Those time points may include week 0 (visit 12 - baseline), week 14 (visit 17 – 2 weeks post 3rd vaccination), week 26

(visit 18 – 2 weeks post 4th vaccination), and/or week 61 (visit 24 – 6 months post 5th vaccination).

Positive response rates will be compared between treatment groups within each time point using Barnard exact test. Titers and AUC-MBs will be compared between treatment groups within each time point using Wilcoxon rank sum test. Positive response rates, titers, and AUC-MBs between time points within treatment group will be also compared using McNemar's tests and Wilcoxon signed rank test, respectively, if neutralizations will be measured at multiple time points.

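### Secondary endpoint 3 is V1V2 IgG breadth, but the SAP's only tabulated and compared per-participant panel summary is AUC-MB, which can hide opposing magnitude and breadth effects

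*SAP*

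**What the plan says.** SAP 3.2 words two of its binding-antibody endpoints differently. Endpoint 1 is "Magnitude and breadth of serum HIV-1 Env-specific IgG responses assessed by Binding Antibody Multiplex Assay two weeks after the last vaccination". Endpoint 3, for Part B, begins "Breadth of gp70-V1V2 IgG and gp120 IgA, assessed by Binding Antibody Multiplex Assay".

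SAP 10.1 then treats the two IgG breadth panels alike: "For each of gp120 breadth panel and gp70 V1V2 breadth panel, magnitude-breadth (MB) and AUC-MB will be calculated for each participant". The between-arm method is "The response magnitudes, AUC-MB will be compared between treatment arms within each timepoint using Wilcoxon rank sum test", and the panel-level entry in SAP 10.1.1 is "The comparisons of AUC-MB between T2 and T3 by isotype, breadth panel, and visit". The SAP also makes a three-condition positivity call for each antigen, compares T2 with T3 on response rate one antigen at a time (Barnard), lists positive responders, and plots magnitude-breadth curves by arm (10.1.2). It does not define, summarise or test how many antigens each participant recognises.

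Protocol 6.4.4.5 says that objectives 1 and 3 both involve magnitude and breadth of IgG to Env panels, and assigns them the neutralization magnitude-breadth methods. Protocol 6.4.4.4 warns that the area-under-the-curve endpoint "may miss an effect wherein 1 vaccine arm has greater magnitude and the comparator vaccine arm has greater breadth", and offers an optional omnibus test of the curves. Protocol 6.4.4.8 names a Kolmogorov-Smirnov type test as an alternative to a Wilcoxon test on AUC-MB. SAP 10.1 contains neither curve test.

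**The concern.** An endpoint stated as breadth is summarised, at panel level, by a number that also rises with magnitude. If one regimen binds fewer V1V2 antigens strongly and the other binds more of them weakly, AUC-MB can come out equal, or higher in the narrower arm.

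V1V2 IgG is measured because it was a correlate of risk in RV144 (Protocol 4.1 and secondary objective 3). Protocol 4.4 says the secondary objectives will rank the regimens and inform whether the formulations advance. T2 receives protein at two visits and T3 at five, so their profiles could differ, although nothing in the documents says in which way. A reader of the final report would have one panel-level comparison for the breadth endpoint, and it might not answer the breadth question.

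**Working it through.** **Inputs from the documents**

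- Panel size, counted from the "gp70 V1V2 Breadth Panel" rows in SAP 10.1: 1 A + 5 B + 7 C + 2 CRF01_AE + 1 CRF07-BC = 16 antigens, all IgG.
- Evaluable n per Part B vaccine arm (Protocol 6.1.2): 21 × (1 − 0.15) = 17.85, which gives the plan's 18.
- Two-sided 0.05 (SAP 8.4.1); Wilcoxon rank sum on AUC-MB (SAP 10.1).
- Meaning of AUC-MB: for neutralization, SAP 10.2 describes it as "which is equivalent to the mean log titer across all viruses in tier 1B and tier 2". The SAP gives no scale for BAMA.

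**Assumptions not in the documents**

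- AUC-MB is the mean log10 net MFI over the 16 antigens.
- Between-participant SD is 0.35 log10 on recognised antigens, and antigen-level SD is 0.30 log10.
- One positivity cutoff at net MFI 300 (log10 = 2.477) stands in for the three-condition rule.
- The MFI levels are those shown below.

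**Step 1: the identity.** Integrating a magnitude-breadth curve numerically for a 16-antigen profile gave 2.7812. The mean log10 value of the same profile was 2.7812.

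**Step 2: the formula.** Suppose a fraction b of antigens sits at log10 level h and the rest at floor f. Then

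AUC-MB = b·h + (1 − b)·f = f + b(h − f).

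It rises with both b and h, so an arm that is ahead on both is ranked first. Arms tie when b(h − f) is equal.

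- Masking, f = log10(100) = 2. 16/16 at MFI 1,000: 2 + 1 × (3 − 2) = 3.00. 8/16 at 10,000: 2 + 0.5 × (4 − 2) = 3.00.
- Reversal, f = log10(50) = 1.699. 16/16 at 1,000: 3.00. 12/16 at 10,000: 1.699 + 0.75 × (4 − 1.699) = 3.42.
- Tipping point for 12/16 against 16/16 at 1,000 with floor 50: h = 1.699 + (3 − 1.699)/0.75 = 3.434, or MFI of about 2,700. The narrower arm needs about 2.7 times the MFI on the antigens it recognises.

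**Step 3: simulation.** 2,000 trials, 18 per arm. Arm A has all 16 antigens centred at MFI 1,000. AUC-MB columns give the percentage of trials significant in favour of each arm.

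| Arm B (narrower) | AUC-MB, A v B | Mean count, A v B | AUC-MB favours A | AUC-MB favours B | Count test significant |
|---|---|---|---|---|---|
| 8 at 10,000, rest 100 | 3.00 v 3.00 | 14.0 v 8.4 | 3.7% | 1.9% | 99.9% |
| 12 at 10,000, rest 50 | 3.00 v 3.42 | 13.9 v 12.0 | 0% | 95.7% | 91.8% |
| 12 at 3,000, rest 50 | 3.00 v 3.03 | 13.9 v 11.8 | 1.5% | 5.1% | 92.6% |
| 12 at 2,000, rest 50 | 3.00 v 2.90 | 13.9 v 11.6 | 14.9% | 0.3% | 93.6% |
| 12 at 1,000, rest 50 | 3.00 v 2.67 | 13.9 v 10.5 | 81.9% | 0% | 97.1% |

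In the first row AUC-MB is significant in 3.7% + 1.9% = 5.6% of trials, close to the nominal error rate. The last row has equal magnitude, and there AUC-MB finds the broader arm in 82%.

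**Step 4: sensitivity to the floor.** In the reversal case, AUC-MB significantly favours the narrower arm in 99.5%, 95.7% and 58.8% of trials for floors of 100, 50 and 10. With a floor of 1 the AUC-MB values tie: 0.75 × 4 + 0.25 × 0 = 3.00.

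**Step 5: how free of magnitude the count is.** In arm A every antigen is recognised, but the total SD is √(0.35² + 0.30²) = 0.461 and (3 − 2.477)/0.461 = 1.13. About 87% of readings therefore pass the cutoff, a mean count of 13.9 and not 16. In a separate run with all 16 antigens recognised in both arms and only magnitude differing (log10 2.9 v 3.3, within-person SD 0.25, cutoff 2.7), mean counts were 10.9 v 14.7 and the count test was significant in 81–83% of trials.

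**The case against.** The strongest reply is that the SAP follows the protocol. Protocol 6.4.4.5 places objective 3 under magnitude and breadth, and 6.4.4.8 lists a Wilcoxon test on AUC-MB as one of two accepted comparisons. This stands. A reader might infer that AUC-MB is the wrong analysis for endpoint 3 or departs from the protocol; the documents do not support that.

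Second, breadth is not otherwise invisible. Curves are plotted by arm, and the 16 response rates sum to each arm's mean count. In an offsetting scenario (50% of antigens at log10 4.0 v 75% at 3.33), per-antigen tests, with Fisher standing in for Barnard, flagged at least one antigen in 100% of trials when all participants recognised the same antigens. When recognition varied at random by person the figure was 86–93%, falling to 21–25% after Bonferroni. So a reader should not infer that the SAP's whole V1V2 output would show no difference. What remains is that 16 unadjusted tests allow up to 16 × 0.05 = 0.8 false flags on average, and give neither a participant-level distribution nor one answer on breadth.

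Third, the failure needs magnitude and breadth to run in opposite directions, and the documents give no evidence that they will. Different protein exposure does not imply such a trade-off. This also stands.

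Fourth, the count depends on its cutoff. True, as step 5 shows, and a reason to report it beside AUC-MB.

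**Conclusion.** The point holds as a gap in the SAP's breadth reporting. Endpoint 3 names breadth, no per-participant breadth number is defined, and the one panel-level comparison has a limitation that the protocol itself states. SAP 10.1 also leaves out both curve tests. Those tests would not fill the gap alone, because they look for any difference between curves and do not isolate breadth.

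Under exactly offsetting effects, AUC-MB has about 5% power and the count over 90%. In the reversal example AUC-MB significantly favours the narrower arm in 96% of trials. These figures rest on assumed MFI levels, SDs, floor and cutoff, and on a log10 scale that the SAP does not state for BAMA. They show what can happen. A reader might infer that this trial is likely to favour the narrower regimen, but the documents give no MFI data from which that chance could be estimated. When the two effects agree, AUC-MB performs well. This is a cheap improvement to a secondary analysis in a phase 1 trial whose primary objective is safety.

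**What to change.** In SAP 10.1, define for each participant the number (0–16) of V1V2 panel antigens with a positive IgG response under the existing three-condition rule. If the cutoff rule removes antigens, use the proportion of those retained. Add to 10.1.1 a table of this score by arm and a T2 v T3 comparison by Wilcoxon rank sum, named as the breadth result for endpoint 3. Report it beside the planned AUC-MB comparison, not in place of it.

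The change needs SAP wording, one table and one test on calls already made, and no new assay work. It should be settled before the unblinded immunogenicity analysis, so that the definition of breadth is not chosen after results are seen. The costs are one more unadjusted secondary comparison and a score that depends on the positivity cutoff, and so partly on magnitude. It does not cover gp120 IgA breadth, which endpoint 3 also names.

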10.1.1 List of Tables

- The binding antibody positive response rates by isotype, antigen, visit and treatment arm
- Summary statistics for magnitudes among the positive responders by isotype, antigen, visit and treatment arm
- Summary statistics for AUC-MB by isotype, breadth panel, visit, and treatment arm
- The comparisons of response rates between T2 and T3 by isotype, antigen, and visit
- The comparisons of response magnitudes between T2 and T3 by isotype, antigen, and visit
- Lists of the positive responders and the magnitudes for those participants
- The comparisons of AUC-MB between T2 and T3 by isotype, breadth panel, and visit
- Geometric mean and 95% CI of titers (EC50/AUC) by isotype, antigen, visit, and treatment arm. 95% CI will be calculated based on a normal approximation for log-transformed titers.
- The comparisons of titers (EC50/AUC) between T2 and T3 by isotype, antigen and visit.
- The comparisons of AUC-MB of titers (EC50/AUC) between T2 and T3 by isotype, breadth panel, and visit

10.1.2 List of Figures

- Boxplots of binding antibody magnitudes by isotype, antigen, visit and treatment arm
- Spaghetti plots of binding antibody magnitudes over time by isotype, antigen, visit and treatment arm
- Magnitude-breadth (MB) curves of binding antibody magnitudes and breadth for a panel of antigens (gp120 breadth panel and gp70 V1V2 breadth panel) by isotype, visit and treatment arm
- Boxplots of binding antibody titers (EC50/AUC) by isotype, antigen, visit and treatment arm
- MB curves of binding antibody titers and breadth for a panel of antigens (gp120 breadth panel and gp70 V1V2 breadth panel) by isotype, visit and treatment arm

10.2 Neutralizing antibody (NAb)

Neutralizing antibodies (NAb) against tier 1A, tier 1B and tier 2 strains of HIV-1 will be measured in TZM-bl cells as a function of reductions in Tat-induced luciferase (Luc) reporter gene expression after a single round of infection with molecularly cloned, Env-pseudotyped viruses. TZM-bl (also called JC57BL-13) is a Hela cell clone that was engineered to express CD4 and CCR5 and to contain integrated reporter genes for firefly luciferase and *E. coli* β -galactosidase under control of an HIV-1 long terminal repeat (LTR). The cells are highly permissive to infection by most strains of HIV, including primary HIV-1 isolates and molecularly cloned Env-pseudotyped viruses. DEAE-dextran is used in the medium during neutralization assays to enhance infectivity. Expression of the reporter genes is induced in trans by viral Tat protein soon after infection. Luciferase activity is quantified by luminescence and is directly proportional to the number of infectious virus particles present in the initial inoculum. The assay is performed in 96-well culture plates for high throughput capacity. Use of a clonal cell population provides enhanced precision and uniformity. The assay has been formally optimized and validated for single-round infection with either uncloned or molecularly cloned Env-pseudotyped viruses produced by transfection in 293T cells.

Assays will be performed using cryopreserved serum sample starting at a specific dilution determined by the lab PI. Titers will be defined as the serum dilution that reduced relative luminescence units (RLU) by 50% and 80% relative to the RLU in the virus control wells after subtraction of background RLU in control wells (ID50 and ID80). Neutralization ID50 and ID80 titers will be measured against MW965.26 (tier 1A vaccine strain), the tier 2 vaccine strains JR-FL and 92UG037.1, and the heterologous tier 1B strains Bx08.16, Q23.17, 6525.3, ZM197M-PB7, and 1056-10.TA11.1826. The global panel and/or clade-specific panels may be used to assess tier 2 neutralization on a selected subset of participants.

A response is considered positive if the neutralization titer is above a pre-specified cutoff. Magnitude of response will be measured by the natural log of the ID50 and ID80 titer. An aggregate measure of response will be calculated as the area-under-the-magnitude-breadth curve (AUC-MB), which is equivalent to the mean log titer across all viruses in tier 1B and tier 2. If a titer is left censored, half the left censor limit will be used as the titer value.

Neutralization titers will be measured on the primary immunogenicity samples at visit 22 (at week 34, 2 weeks post the 5th vaccination) from all 48 Part B participants. Specimens from other time points may also be analyzed at the discretion of the HVTN Laboratory Program, which may be contingent on the results of the primary immunogenicity time point. Those time points may include week 0 (visit 12 - baseline), week 14 (visit 17 – 2 weeks post 3rd vaccination), week 26

(visit 18 – 2 weeks post 4th vaccination), and/or week 61 (visit 24 – 6 months post 5th vaccination).

Positive response rates will be compared between treatment groups within each time point using Barnard exact test. Titers and AUC-MBs will be compared between treatment groups within each time point using Wilcoxon rank sum test. Positive response rates, titers, and AUC-MBs between time points within treatment group will be also compared using McNemar's tests and Wilcoxon signed rank test, respectively, if neutralizations will be measured at multiple time points.

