
6.4.4.3 Primary analyses of neutralization magnitude-breadth curves

Separate analyses of magnitude-breadth of neutralization will be conducted for the Tier 1B isolate panel and for the Tier 2 isolate panel, for all analyses whether primary, secondary, or exploratory.

For each panel, individual magnitude-breadth curves will be plotted by vaccine arm and pooled placebo, with average magnitude-breadth curves overlaid on the plots. For each panel, the area-under-the-magnitude-breadth curve (AUC-MB) (61) will be computed for each participant, as described in (62). Dunnett’s procedure will be applied with 2-sided alpha = 0.05 to determine which of the two vaccine arms have a significantly higher mean AUC-MB than that of the pooled

placebo groups, as described in (63) (see their formula (1.1)). This procedure will be applied to construct 95% CIs about the 2 differences in mean AUC-MB for each vaccine regimen versus the pooled placebos (vaccine – placebo), which simultaneously have at least 95% coverage probability.

The vaccine regimens will be ranked by the estimated mean of the AUC-MB curves. The vaccine regimen with the highest estimated mean will be selected as the best regimen.

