10.5.2 Neutralizing antibody assay (Part B)

HIV-1-specific nAb assays will be performed on serum samples from study participants taken at the primary immunogenicity timepoint(s). Specimens from the baseline and other timepoints may also be analyzed at the discretion of the HVTN Laboratory Program, which may be contingent on the results of the primary immunogenicity timepoints. The TZM-bl assay will test neutralization of the vaccine strains and at least one highly neutralization-sensitive tier 1A virus. The global panel and/or clade-specific panels may be used to assess tier 2 virus neutralization (61, 66). Additional TZM-bl assays may be performed to test neutralization of Tier 1B strains.

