10.2.1 List of Tables

- The NAb positive response rates by cell type, isolate, visit and group.
- Lists of the positive responders and the titer for those participants.
- Summary statistics for NAb titers among the positive responders.
- The comparisons of response rates between groups by cell type, isolate, and visit.
- The comparisons of titers between groups by cell type, isolate, and visit.
- The comparison of AUC-MB between groups by visit

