10.2.2 List of Figures

- Boxplots of neutralizing antibody titers by cell type, isolate, visit, and group.
- Spaghetti plots of neutralizing antibody titer over time by cell type, isolate, and group
- Reverse CDFs of neutralizing antibody titers by cell type, visit and group
- Magnitude-breadth (MB) plots of titer and breadth for a panel of viruses by cell type, visit, and group

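### SAP 10.2 pools tier 1B and tier 2 viruses into one neutralization AUC-MB, although protocol 6.4.4.3 requires the two tiers to be analysed separately

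*SAP*

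**What the plan says.** Protocol 6.4.4.3: "Separate analyses of magnitude-breadth of neutralization will be conducted for the Tier 1B isolate panel and for the Tier 2 isolate panel". The sentence goes on to cover primary, secondary and exploratory analyses alike. The section then computes AUC-MB per participant for each panel and picks the better regimen by the higher mean AUC-MB.

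SAP 10.2 describes one aggregate measure, the AUC-MB, "which is equivalent to the mean log titer across all viruses in tier 1B and tier 2". The viruses it names for these tiers are "the tier 2 vaccine strains JR-FL and 92UG037.1, and the heterologous tier 1B strains Bx08.16, Q23.17, 6525.3, ZM197M-PB7, and 1056-10.TA11.1826". One tier 1A strain is also tested but lies outside the aggregate. Wider tier 2 testing is optional: "The global panel and/or clade-specific panels may be used to assess tier 2 neutralization on a selected subset of participants". Protocol 10.5.2 likewise makes it optional, without restricting it to a subset: "The global panel and/or clade-specific panels may be used to assess tier 2 virus neutralization".

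The SAP's neutralization outputs are "The comparison of AUC-MB between groups by visit" (10.2.1) and "Magnitude-breadth (MB) plots of titer and breadth for a panel of viruses by cell type, visit, and group" (10.2.2). Neither names a tier. For binding antibody the SAP does split the score: "The comparisons of AUC-MB between T2 and T3 by isotype, breadth panel, and visit" (10.1.1). Titers and response rates for neutralization are compared isolate by isolate (10.2.1).

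**The concern.** The two documents define different endpoints, and the SAP gives no reason for departing from the protocol. Because the SAP splits AUC-MB by panel for binding antibody, the missing split for neutralization cannot be read as a general shorthand.

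AUC-MB is the aggregate measure for secondary endpoint 2. Protocol 4.4 makes neutralizing antibody one of the main immunogenicity outcomes, and 4.4.1 cites tier 2 neutralization when justifying the size of Part B. A pooled mean can miss a difference between T2 (prime-boost) and T3 (co-administration) that lies only in tier 2. It can also be significant because of tier 1B alone. In neither case does the score show which tier is responsible. With both texts in force, the choice of aggregate definition could also be made after unblinding.

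**Working it through.** **The texts side by side.** The protocol requires two scores per participant, one per tier, with a ranking on each. The SAP provides one score over both tiers and one comparison per visit. No tier-specific neutralization AUC-MB is listed anywhere in the SAP.

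**Inputs from the documents.** Five tier 1B and two tier 2 viruses (SAP 10.2); 18 evaluable per vaccine arm, from 21 enrolled with 15% missing (protocol 6.1.2); Wilcoxon rank sum test (SAP 10.2), two-sided at 0.05 (SAP 8.4.1); normal log titers with a common SD (protocol 6.1.2).

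**Assumptions, because the documents give no figures.** Equal SD for every virus; the same correlation ρ between any two viruses, taken as 0.3, 0.5 and 0.7; no censoring.

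**The plan's nearest figure.** The documents give no power for AUC-MB. The closest is Table 6-6, 100% response-rate row: 1.1 SD for 80% power and 1.3 SD for 90%. With 18 per arm and the exact Wilcoxon test, I get 87.6% and 95.5% at those differences, and detectable differences of about 1.0 and 1.15 SD. The row is therefore conservative and not reproduced; 15 per arm nearly matches it (79.3% and 91.2%). This does not affect the present point.

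**Weight of tier 2.** 2/(5+2) = 0.29. If tier 2 shifts by d and tier 1B does not, the pooled mean shifts by (2/7)d.

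**Standardized effect of a 1-SD shift confined to tier 2.**
- Pooled: (2/7) ÷ √[(1+6ρ)/7] = 0.45, 0.38, 0.33 for ρ = 0.3, 0.5, 0.7.
- Tier 2 score: 1 ÷ √[(1+ρ)/2] = 1.24, 1.15, 1.08.

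**Power** (simulation, 10,000 replicates; range over ρ = 0.3 to 0.7):

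| True shift, tier 1B / tier 2 | Pooled AUC-MB | Tier 2 AUC-MB |
|---|---|---|
| 0 / 1 SD | 15–24% | 86–94% |
| 0.5 / 1 SD | 55–82% | 86–94% |
| 1 / 1 SD | 91–99% | 86–93% |
| 1 SD / 0 | 64–89% | 4–5% |
| −0.4 / 1 SD | about 5% | 87–94% |

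In the last row the pooled difference is exactly zero: [5 × (−0.4) + 2 × 1]/7 = 0.

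**A different scaling.** If the tier 2 difference is set at 1.0 to 1.1 SD of the tier 2 score itself, and between-tier correlation may fall to 0.1, the tier 2 score has 80–87% power and the pooled score 13–23%.

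**Optional tier 2 panels.** The SAP does not say whether their results enter the score. If 6 to 12 extra viruses (assumed; no panel size is given) entered for a subset, tier 2's weight in those participants would be (2+6)/13 = 62% to (2+12)/19 = 74%, against 29% in the others. Their scores would not be comparable.

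**The case against.** The strongest reply is that the SAP keeps comparisons by isolate, and only two tier 2 viruses are tested in everyone. In the tier 2-only case each isolate test has about 80% power, and at least one of the two is significant in about 89–94% of trials, much the same as for the tier 2 score. When the tier 2 score is significant, at least one isolate test is too in 98–99% of trials. The two unadjusted tests have a null rate of roughly 8–9%, and the comparison assumes titers are compared in all participants rather than responders only. This stands: the SAP as a whole is not blind to tier 2, and the isolate tables can show where a difference lies. They do not supply the per-panel AUC-MB or the ranking that the protocol requires.

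Pooling also gains power when both tiers shift by 1 SD, and the documents do not say that a tier 2-only shift is the likely case. That stands too.

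The absolute powers are optimistic if tier 2 titers are often censored. Protocol 4.8.1 reports that most sera in the predecessor trial inhibited tier 2 viruses by less than 50% at 1:10. If 90% of control-level tier 2 titers are assumed censored, the tier 2 score falls to 68–78% and the pooled score to 7–9%. The direction is unchanged.

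The point about optional panels is conditional and amounts to a request for clarification. Finally, SAP section 1 foresees revisions for immunogenicity and nothing in the SAP claims to override the protocol. That makes the correction easy; it does not remove the conflict.

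**Conclusion.** The concern holds and should be fixed. It rests on a direct contradiction between protocol 6.4.4.3 and SAP 10.2, which no calculation is needed to establish. Following the SAP as written would report an aggregate that the protocol rules out and omit the two that it requires.

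The 2/7 weight follows from the named strains. The contrast of 15–24% with 86–94% depends on the assumed shift, correlations, equal SDs and absence of censoring; it illustrates the possible loss and is not a forecast. The damage is limited to the aggregate score and the ranking based on it.

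**What to change.** - In SAP 10.2, replace the pooled definition with one AUC-MB for tier 1B and one for tier 2, each over a fixed, named virus list tested in every participant included.
- Add tier or panel to the AUC-MB table (10.2.1) and the magnitude-breadth figure (10.2.2), and rank the regimens per panel as the protocol does.
- Report any global or clade-specific panel run on a subset as its own AUC-MB, and state that it does not enter the main scores.
- State that the tier 2 list tested in everyone is currently the two vaccine strains, so its score says little about tier 2 breadth.
- Keep a pooled score, if wanted, only as a labelled supplementary summary. If pooling is intended as the main measure, amend the protocol and give the reason.
- State that the two tier tests are unadjusted, in line with the plan for secondary endpoints. If independent, their joint error rate is 1 − 0.95² = 9.75%.
- For reporting, align the SAP's natural log with the protocol's log10; the base does not change the Wilcoxon tests.

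The cost is SAP wording plus a tier split of one existing table and one figure per visit. No new assays are needed. Wider tier 2 breadth in all participants would require running the optional panels on everyone, which is a separate decision.
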